Developing an LC-MS/MS method for measurement of tacrolimus and creatinine concentration from finger-prick blood collected using the Mitra device

RESEARCH REFERENCE NUMBERS

IRAS Number: 340380

SPONSORS Number: Generated by the Sponsor. Enter if applicable

FUNDERS Number: Generated by the funder. Enter if applicable

VERSION NUMBER AND DATE: Version 0.1 (29-08-2024)

Statistical Analysis Plan

Hypothesis:

The LC-MS/MS method for the quantitation of creatinine and tacrolimus in finger-prick samples collected from the Mitra device will produce results that are not statistically different from whole blood venous samples.

Methodology

[figure not shown]
Patients attending the Nottingham renal clinic for routine therapeutic drug monitoring for Tacrolimus will be consented to have a venous blood sample and a corresponding finger-prick sample (collected using the Mitra device) collected for tacrolimus and creatinine analysis (please see flowchart below).

50 samples will be collected from consented patients. The tacrolimus levels from the venous blood samples will be measured using the routine LC-MS/MS method and creatinine will be measured using the Abbott enzymatic creatinine method. The capillary-finger-prick samples collected using the Mitra device will be analysed using the optimised LC-MS/MS methods for creatinine and tacrolimus.

[figure not shown]
The results from the venous blood samples will be reported following routine laboratory processes (direct transfer of results from laboratory LIMS system to the electronic patient record). These results will then be transferred onto a password-protected spreadsheet accessible only by the investigators of the study. All data will be depersonalised. No patient identifiers will be taken from the electronic patient record – only the sample number, tacrolimus result, and creatinine result will be required. The results from the Mitra-collect finger-prick samples will be transferred to the same password-protected spreadsheet accessible only by the investigators of the study. These results will not be transferred to any patient record.

Results of the Mitra-device collected samples and venepuncture collected samples will be compared. The data collected will be analysed using the 'Analyse-It' statistics software and Bland-Altman and Passing-Bablok regression analyses will be completed to identify any statistical differences between the two LC-MS/MS methods. Research data (excluding patient details) will be stored in the Laboratory Quality Management System (Q-Pulse).

[figure not shown]
Participant recruitment

Mitra-collected samples

Venepuncture-collected samples

Method comparison

Results of the Mitra-device collected samples and venepuncture collected samples will be compared. The data collected will be analysed using the 'analyse-it' statistics software. Research data (excluding patient details) will be stored in the Laboratory Quality Management System (Q-Pulse).

Results

Please see Flowchart for details of participant flow.

Patients will be recruited and consented by the renal clinical team. Patient Information leaflets will be distributed to all volunteers and consent forms signed by the participants or parents/carers for paediatric patients. 50 patients will be included in the study and the results from the venous blood and capillary-finger prick samples compared.

The results from the venous blood samples will be processed and reported using the normal laboratory processes (electronic transfer of results from the laboratory LIMS system to the electronic patient record), ensuring there is no delay in receipt of routine results. As the results from the finger-prick blood samples collected using the Mitra device will not be reported there will be no change to tacrolimus dosing regimens based on these results. There are no anticipated adverse events expected.

Results of the Mitra-device collected samples and venepuncture collected samples will be compared. The data collected will be analysed using the 'Analyse-It' statistics software and Bland-Altman and Passing-Bablok regression analyses will be completed to identify any statistical differences between the two LC-MS/MS methods. Research data (excluding patient details) will be stored in the Laboratory Quality Management System (Q-Pulse).

Interpretation

Results of the Mitra-device collected samples and venepuncture collected samples will be compared. The data collected will be analysed using the 'Analyse-It' statistics software and Bland-Altman and Passing-Bablok regression analyses will be completed to identify any statistical differences between the two LC-MS/MS methods. Research data (excluding patient details) will be stored in the Laboratory Quality Management System (Q-Pulse).

The statistical analysis of the results will be compared to those previously reported by the Wythenshawe Laboratory (Marshall et Al. 2020) who have also introduced a finger-prick capillary collection method for tacrolimus and creatinine. The outcome of this study will be disseminated to the renal clinical team. If no statistically significant difference is identified between the methodologies, it is anticipated that the Mitra-devices could be utilised for remote blood collection and samples sent to the laboratory via postal services for tacrolimus and creatinine measurement. This would reduce the number of outpatient appointments required for patients requiring therapeutic drug monitoring.

References

Marshall, D. J., Kim, J. J., Brand, S., Bryne, C., & Keevil, B. G. (2020). Assessment of tacrolimus and creatinine concentration collected using Mitra microsampling devices. *Annals of Clinical Biochemistry*, 57(5), 389-396

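### Do '50 samples' in one place and '50 patients' in another leave the independence of the pairs in doubt?

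*SAP*

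**What the plan says.** Under Methodology the SAP states that "50 samples will be collected from consented patients". The paragraph just before it describes what each participant gives: patients "will be consented to have a venous blood sample and a corresponding finger-prick sample". Under Results the same number appears with a different noun: "50 patients will be included in the study and the results from the venous blood and capillary-finger prick samples compared".

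The participants are "Patients attending the Nottingham renal clinic for routine therapeutic drug monitoring for Tacrolimus", so some could return to the clinic during recruitment. On data handling, Methodology says that "All data will be depersonalised" and that, from the electronic patient record, "only the sample number, tacrolimus result, and creatinine result will be required". Results and Interpretation add that "Research data (excluding patient details) will be stored in the Laboratory Quality Management System (Q-Pulse").

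The analysis is stated in one sentence: "Bland-Altman and Passing-Bablok regression analyses will be completed to identify any statistical differences between the two LC-MS/MS methods". No version for repeated pairs is named.

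**The concern.** A sample count and a patient count are different quantities. Read alone, the Methodology sentence would allow 50 pairs from fewer than 50 patients, or 50 single specimens making 25 pairs. The SAP has no power or precision calculation from which the intended unit could be recovered.

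The unit matters because the standard forms of both planned analyses assume independent pairs. If one patient's paired differences resemble each other, for example through a stable haematocrit effect or sampling technique, then treating repeat pairs as separate makes confidence intervals too narrow. If there were only 25 pairs, the intervals would be wider, and under Interpretation the absence of a significant difference is what supports use of the device. With no patient-level field among those listed, an analyst working from the listed fields alone could not see repeats. At stake would be the precision and error rate of the study's only comparison.

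**Working it through.** **Can the 50 be reproduced?** No. The SAP gives no significance level, power, SD of differences or acceptance limit, so the number can only be checked by counting.

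**Counting check.** Inputs: 50 patients (Results); one venous and one matching finger-prick sample per patient (Methodology, singular wording).

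- Pairs: 50 × 1 = 50. Specimens: 50 × 2 = 100.
- If the Methodology figure means sample pairs, it is 50 and agrees with Results.
- If it means single specimens, there are 50 / 2 = 25 pairs. That cannot be squared with 50 patients who each provide both results.
- If it means 50 pairs with repeats, there are fewer than 50 patients, which again contradicts Results.

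Only the first reading satisfies all three statements.

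**Precision on that reading.** In units of the SD of the paired differences, with n = 50 and t(0.975, 49) = 2.010:

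- bias: t/√n = 2.010/√50 = 0.284
- limit of agreement: t × √(1/n + 1.96²/(2(n−1))) = 2.010 × √(0.0200 + 0.0392) = 0.489

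For 25 pairs, with t(0.975, 24) = 2.064, these become 0.413 and 0.715.

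**What repeats would do.** Pairs per patient (m) and the within-patient correlation of differences (ICC) are assumptions; the SAP gives neither. The design effect is DE = 1 + (m−1) × ICC, the effective number of pairs is 50/DE, and the true error of a naive two-sided 5% test of zero bias is 2 × (1 − Φ(1.96/√DE)).

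| Patients × pairs | ICC | DE | Effective n | True error |
|---|---|---|---|---|
| 50 × 1 | any | 1.0 | 50 | 5.0% |
| 25 × 2 | 0.3 | 1.3 | 38.5 | 8.6% |
| 25 × 2 | 0.5 | 1.5 | 33.3 | 11.0% |
| 25 × 2 | 0.8 | 1.8 | 27.8 | 14.4% |
| 10 × 5 | 0.5 | 3.0 | 16.7 | 25.8% |

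Simulated t-tests (100,000 runs each) gave 8.5%, 10.9%, 14.7% and 26.6% for the last four rows, so the approximation is sound. These figures concern the bias test only; no equivalent was computed for Passing-Bablok.

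**Direction.** Inflated error from clustering produces more false differences, which counts against the device under the Interpretation rule. Only the 25-pair reading makes a favourable conclusion easier, and it is the reading with least support in the text.

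**Patient code.** The restriction in Methodology concerns what is taken from the electronic patient record. It does not list every column of the study spreadsheet, and it neither provides nor excludes a pseudonymous study number. Matching each finger-prick result to its venous result needs some linking key in any case. The sample number is kept, and venous results pass through the laboratory system to the patient record, so a repeat patient may be traceable, although no such check is described.

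**The case for a change.** The strongest case for a change is that the unit of analysis belongs in the SAP, that the document never says a patient contributes once, and that recruitment takes place in a clinic patients revisit. A team working to a count of samples could enrol someone twice without breaching that sentence. The arithmetic is correct as far as it goes, and the remedy is cheap: one sentence and one pseudonymous column in a document still at Version 0.1.

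Part of this stands. The unit is not fixed in so many words, no one-pair rule is written, and no patient-level field is described. But the sentence about samples does not stand alone. Following it into repeat sampling means disregarding the patient count under Results, and nothing in the SAP plans or mentions a second pair from anyone. The renal clinical team recruits participants and obtains signed consent, so it is well placed to know who has already taken part. Low cost is not in itself a reason to change a plan when the new words would produce the same 50 pairs and the same analysis.

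**Conclusion.** The concern does not call for a change. The SAP uses a loose noun in one sentence, and its neighbouring statements resolve it to 50 patients with one venous and finger-prick pair each. Conducted that way, the pairs are independent, the nominal 5% error is kept, and the half-widths are 0.28 SD for bias and 0.49 SD for each limit of agreement. An explicit one-pair sentence would record what the plan already implies and alter no result.

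This rests on taking the singular description of what each patient gives, and the patient count under Results, at face value. If repeat pairs were in fact taken, the error rates in the table would become relevant and an analysis allowing for clustering would be needed. The SAP does not plan for that to happen. The stronger claims, that no patient code exists and that repeats could never be found, go beyond the text.

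### Does calling the comparison one between two LC-MS/MS methods leave creatinine, whose venous comparator is enzymatic, without a valid analysis?

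*SAP*

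**What the plan says.** The Methodology section assigns the assays. For venous blood, "The tacrolimus levels from the venous blood samples will be measured using the routine LC-MS/MS method", while "creatinine will be measured using the Abbott enzymatic creatinine method". The finger-prick samples, for both analytes, "will be analysed using the optimised LC-MS/MS methods for creatinine and tacrolimus".

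The purpose of the analyses is stated in the paragraph that closes Methodology before the flowchart, again under Results, and once more under Interpretation: "Bland-Altman and Passing-Bablok regression analyses will be completed to identify any statistical differences between the two LC-MS/MS methods". Each time the sentence follows a plainer one: "Results of the Mitra-device collected samples and venepuncture collected samples will be compared". The paragraph under Method comparison has the plainer sentence without the LC-MS/MS phrase.

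The Hypothesis covers both analytes and sets the Mitra LC-MS/MS result against venous samples, without saying how the venous samples are assayed. Results gives the size: "50 patients will be included in the study and the results from the venous blood and capillary-finger prick samples compared". Interpretation then makes possible remote use for both analytes conditional: "If no statistically significant difference is identified between the methodologies".

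**The concern.** Read literally, the analysis sentence describes a comparison that cannot be made for creatinine, because the SAP lists no venous LC-MS/MS creatinine result. The creatinine pairs differ both in how the blood is collected and in assay principle. A bias could come from the finger-prick and device step, from LC-MS/MS against enzymatic measurement, or from both, and the two parts could offset each other. The planned pairs cannot separate them. If the creatinine bias, slope and intercept were reported as differences between two LC-MS/MS methods, the report would be untrue, and a reader might take the whole difference as an effect of the device.

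A second worry is that Interpretation states a single condition for two analytes with different comparators, and does not say what follows if one agrees and the other does not.

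**Working it through.** The SAP gives no figure to reproduce on this point. The check sets the assay assignments beside the description of the analysis.

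**Assays, from Methodology**

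| Analyte | Finger-prick (Mitra) | Venous | Two LC-MS/MS methods? |
|---|---|---|---|
| Tacrolimus | optimised LC-MS/MS | routine LC-MS/MS | yes |
| Creatinine | optimised LC-MS/MS | Abbott enzymatic | no |

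**Extent of the mislabel**

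- Places: end of Methodology 1 + Results 1 + Interpretation 1 = 3. These are all the paragraphs that name the Bland-Altman and Passing-Bablok analyses, and they repeat the same text.
- Pairs: assuming one pair per analyte per patient, 50 × 2 = 100, of which 50 are creatinine; 50/100 = 50%. This restates one analyte in two. It does not measure an effect on any result.

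**Can the phrase mean something else?** It cannot be confined to tacrolimus, since the Hypothesis and Interpretation both include creatinine. It cannot mean the Mitra tacrolimus assay against the Mitra creatinine assay, since agreement between different analytes has no meaning. So it is a genuine misdescription for creatinine.

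**Does it alter what is calculated?** For patient *i*, the creatinine difference is

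*d*ᵢ = (Mitra LC-MS/MS result)ᵢ − (venous result)ᵢ.

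The only venous creatinine result in the plan is the enzymatic one. The Bland-Altman bias and limits of agreement are the mean of *d* and the spread around it, and the Passing-Bablok slope and intercept come from the same 50 pairs. The name given to the comparator enters none of these.

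**Does it alter what is concluded?** For either analyte the expected difference can be written as

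total difference = collection part + assay part.

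Interpretation asks whether Mitra samples could be used for remote collection in place of clinic attendance. That turns on the total, because the total is what separates a Mitra result from the routine result it would replace. If the two parts offset each other, the total still answers that question. Separating them would matter only for a claim about the device by itself, and the SAP makes none. The condition in Interpretation speaks of methodologies, a term that fits LC-MS/MS against enzymatic as well as LC-MS/MS against LC-MS/MS.

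**Is creatinine a special case?** Only in degree. Methodology distinguishes a routine from an optimised LC-MS/MS method for tacrolimus, so those pairs also combine a collection part and an assay part. A caveat attached to creatinine alone would wrongly suggest that a tacrolimus difference could be put down to the device.

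**The single condition.** Bland-Altman and Passing-Bablok have to be run separately for tacrolimus and creatinine, because pooling two analytes would make no sense. The results therefore arrive separately. This point would arise even if both comparators were LC-MS/MS, so it does not follow from the mislabel.

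**The case for a change.** The strongest case for a change is that a SAP should say correctly what its estimates mean, and this one does not for creatinine, in identical words in three places. The text is current and complete. The conflict lies within the document, so it cannot be left to a protocol. The document is marked Version 0.1, so correcting it would cost nothing but wording, whereas redefining the creatinine claim later would be done with the data in view.

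The misdescription stands and is conceded. The rest carries less weight. The creatinine claim would not need redefining later, because the Hypothesis already states it as the Mitra procedure against venous results and Methodology already names the enzymatic comparator. Anyone writing up the study must state the venous creatinine assay in the methods, and the slip would show at once. The lack of a stated rule for discordant analytes is real, but Interpretation is tentative about what could follow and is not a formal decision rule. Investigators would naturally report the two analytes side by side.

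**Conclusion.** A clerical slip: the phrase "to identify any statistical differences between the two LC-MS/MS methods" is accurate for tacrolimus and inaccurate for creatinine. The creatinine comparison exists, is identifiable from Methodology, and is suited to the replacement question. Correcting the label would change none of the pairs, estimates or planned conclusions, so no change to the plan is called for.

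This rests on two readings of the SAP: that the enzymatic result is the only venous creatinine measurement, as Methodology states, and that the aim is agreement with the routine venous result, as the Hypothesis and Interpretation indicate. If the report set out to isolate the effect of the device, the pairs would not support that for creatinine, nor cleanly for tacrolimus. Whether absence of a significant difference is a good criterion for agreement is a separate question and is not judged here.

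### Does testing two analytes with several unadjusted checks, and drawing one conclusion from them, call for a multiplicity rule in the SAP?

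*SAP*

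**What the plan says.** The Hypothesis section makes one statement for both analytes: "the quantitation of creatinine and tacrolimus in finger-prick samples collected from the Mitra device will produce results that are not statistically different" from venous results. The Results section fixes the size, "50 patients will be included in the study", with one venous and one finger-prick sample compared per patient.

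The analysis sentence appears under Methodology, Results and Interpretation: "Bland-Altman and Passing-Bablok regression analyses will be completed to identify any statistical differences" between the two methods. The Interpretation section then gives the consequence. "If no statistically significant difference is identified between the methodologies", the SAP anticipates that the device could be used remotely, with "samples sent to the laboratory via postal services for tacrolimus and creatinine measurement". The same section also says that the statistical results will be compared with those reported by another laboratory, and that the outcome will go to the renal clinical team.

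The SAP states no significance or confidence level, does not list which parameters are tested, gives no rule for combining the two analyses, and does not say whether the conclusion is drawn once or per analyte.

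**The concern.** Each analyte would normally yield three significance results: the Bland-Altman mean difference against 0, the Passing-Bablok slope against 1 and the Passing-Bablok intercept against 0. With two analytes that makes six. The SAP looks for any difference and draws one conclusion, so on a literal reading a single excluded value among the six blocks it. A reader who assumes a 5% chance of a false alarm would be wrong by a factor of about four, and a finger-prick method that agrees on average with the venous method could be reported as different by chance.

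The obvious remedy is to name one deciding result per analyte (for example the Bland-Altman mean difference on a named scale), make Passing-Bablok supportive, and use 97.5% intervals if the two analytes share one conclusion.

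**Working it through.** The SAP gives no error rate, power or sample-size calculation, so there is no figure of its own to reproduce.

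**Inputs.** From the SAP: n = 50 pairs, two analytes, two analyses. Assumed: two-sided 5% per check; three checks per analyte; error proportional to concentration unless stated; SD of the differences 10% in steps 3 to 5. The ranges in steps 3 to 5 are also assumed: tacrolimus 3-15 or 6-12, creatinine 40-400.

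**1. Bound from independence.** The chance of at least one false flag in k independent checks is 1 − 0.95^k:
- k = 2: 9.75%
- k = 4: 18.55%
- k = 6: 26.49%

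The three checks on one analyte are correlated, so the six-check figure is a rough guide only.

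**2. Simulation, equal methods.** This used a paired t interval for the mean difference and rank-based 95% intervals for slope and intercept, with 4,000-5,000 data sets per setting. Method CVs were 5-12% and the log-SD of concentration was 0.35-0.5.
- Proportional error: 10-12% flagged per analyte, 19-22% for the pair.
- Constant error: 12-15% per analyte, 22-27% for the pair.
- Worked example: 11.3% per analyte gives 1 − (1 − 0.113)² = 21.3%.
- Finger-prick error correlated between analytes (0 to 1), equal CVs: 20-22%.

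So about 1 in 5 is right under these assumptions. With only the mean difference and slope counted it is 17-20%; with Passing-Bablok alone, 13-20%.

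**3. What a single deciding result would do to false alarms.** Two checks at 5% give 1 − 0.95² = 9.75%; two at 2.5% give 1 − 0.975² = 4.9%. The inflation goes away.

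**4. What it would do to detection of bias that changes sign over the range.** Take tacrolimus 3-15 with slope 1.2 and intercept −1.21. At 3 the finger-prick result is 1.2 × 3 − 1.21 = 2.39, or −20%. At 15 it is 1.2 × 15 − 1.21 = 16.79, or +12%. The percentage differences roughly cancel on average.

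| Scenario | Bland-Altman, percent scale, 5% | Passing-Bablok |
|---|---|---|
| Tacrolimus 3-15, slope 1.2, intercept −1.21 | 4.8% | 100% |
| Creatinine 40-400, slope 1.15, intercept −15 | 5.6% | 99.8% |
| Tacrolimus 6-12, slope 1.2, offset balancing the mean | 4.6% | 71% |

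Across repeat runs the mean difference alone flags these in about 5-7%. Counting either analysis flags them in 72-100%.

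**5. What it would do to a uniform 3% bias.** Counting any check detects it in 54-61% of studies; the percent-scale mean difference alone at 5% in 54-55%; the same at 2.5% in 40-43%.

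**6. Direction.** The Interpretation section moves towards postal use when no difference is found. Wider intervals, or fewer results that count, make that outcome easier to reach. The errors reduced in step 3 are false rejections of equal methods; those increased in steps 4 and 5 are failures to see a real bias.

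**The case for a change.** The strongest argument for a change is that the Interpretation section states a conditional conclusion without saying which result decides it, and that on every plausible count of checks the false-alarm rate is well above 5%. A few lines of text, before any data are seen and at no cost in samples, would settle it. The arithmetic behind this stands, and so does the point that the interval level and the unit of conclusion are unstated.

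Two supporting arguments are weaker. The first is that the SAP could be read as requiring both analyses to show a difference, so that a 10% bias over a narrow tacrolimus range would be missed in 74% of studies, because Passing-Bablok flags it in only 26%. The SAP looks for any difference, and nothing in it supports a both-must-agree rule.

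The second is that the joint false-alarm rate rises to 27-30% (range 3-15) or 40-42% (range 6-12) if the finger-prick method is noisier (CV 9.5% against 3%). That is mostly not multiplicity. Over 6-12, Passing-Bablok alone then flags about 27% of equal methods, because unequal imprecision breaks its assumption, while Bland-Altman stays near 5%. A multiplicity rule does not address that.

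It is also fair to say that a SAP could keep both analyses and still state how they combine. But the SAP describes an appraisal of agreement, softly worded, compared with another laboratory's results and passed to the clinical team. It is not a formal test procedure whose overall error rate has to be held at a set level.

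**Conclusion.** No change follows from this point. The rate of about 1 in 5 is correct if each of six checks is read at two-sided 5% and any one counts; the SAP states neither. The error it describes, turning down a finger-prick method that is in fact equal, is the less harmful one here. Making the mean difference decide alone would give up nearly all ability to see a bias that changes sign over the range (about 5-7% flagged instead of 72-100%), and widening the intervals would lower detection of a 3% bias to 40-43%. At best that is a trade-off, and it works against the cautious direction.

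The remaining gap, the interval level and a result for each analyte, is one analysts fill sensibly. Both analyses have to be run separately for tacrolimus and creatinine anyway, and their estimates with confidence intervals can be read side by side.

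Treating a non-significant result as evidence of agreement is a different question. It is not settled here, and a multiplicity adjustment would make it worse. These conclusions rest on the assumed ranges, error sizes and 5% level given in the working.

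### The SAP takes absence of a statistically significant difference as proof that finger-prick and venous results agree, and sets no limit for acceptable disagreement

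*SAP*

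**What the plan says.** Three statements in the SAP set the standard.

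- **Hypothesis:** the finger-prick method "will produce results that are not statistically different from whole blood venous samples".
- **Purpose of the analyses** (the method-comparison text, repeated under Results and Interpretation): "Bland-Altman and Passing-Bablok regression analyses will be completed to identify any statistical differences".
- **Condition for remote use** (Interpretation): "If no statistically significant difference is identified between the methodologies, it is anticipated that the Mitra-devices could be utilised for remote blood collection".

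The sample is given under Results: "50 patients will be included in the study and the results from the venous blood and capillary-finger prick samples compared". Interpretation adds one external reference point: "The statistical analysis of the results will be compared to those previously reported by the Wythenshawe Laboratory". No threshold is attached to that comparison. For neither tacrolimus nor creatinine does the SAP give a significance level, a margin, an acceptable bias, acceptable limits of agreement, or acceptable limits for slope and intercept.

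**The concern.** A non-significant test says that the data do not rule out zero difference. It does not say that the difference is small, and it says nothing about the spread of individual differences. That spread is what matters if one finger-prick result is to stand in for one venous result. Bland-Altman analysis will produce limits of agreement, but the SAP gives nothing to judge them against and states its aim as finding differences.

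Two errors follow. A widely scattered method can be supported because its noise hides a bias or because its mean bias is near zero. A tight method with a small bias that could be corrected can contradict the hypothesis. At stake is the study's central inference, since Interpretation links this result to postal sampling and fewer outpatient visits.

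**Working it through.** **Inputs.** From the SAP: 50 patients, read as 50 venous/finger-prick pairs. The SAP derives this number from nothing, so it cannot be reproduced, and the point does not depend on it. Assumed, because the SAP is silent: two-sided 5% tests, percent differences, SD of differences from 5% to 30%, and true bias of 0% or 3%.

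**Step 1: precision with 50 pairs.** t(0.975, 49) = 2.0096.

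- Half-width of the 95% CI for mean bias: 2.0096/√50 = 0.284 SD.
- Half-width for each limit of agreement: 2.0096 × √(1/50 + 1.96²/(2 × 49)) = 0.489 SD.

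**Step 2: Bland-Altman bias test alone.** The chance of non-significance comes from the noncentral t distribution with 49 df and noncentrality bias × √50/SD. At 3% bias it is 0.014, 0.452, 0.716 and 0.820 for SD 5, 10, 15 and 20%. At zero bias it is 0.95 whatever the SD. Smaller studies also pass more easily: at 5% bias and SD 15% the chance is 0.84 with 10 pairs, 0.36 with 50 and 0.09 with 100.

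**Step 3: both planned analyses.** A pass is taken as a non-significant t-test on percent differences, a Passing-Bablok slope CI containing 1 and an intercept CI containing 0. The simulation used 3,000 replicates per cell (standard error under 1 percentage point). True values were uniform over assumed ranges (tacrolimus 4-15, creatinine 40-400) with proportional normal errors. Venous CV was 4% and Mitra CV was √(SD² - 4²).

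| Pass rate at SD of differences | 5% | 10% | 15% | 20% | 30% |
|---|---|---|---|---|---|
| Tacrolimus, bias 3% | 1% | 45% | 54% | 44% | 16% |
| Tacrolimus, bias 0% | 89% | 84% | 69% | 51% | 18% |
| Creatinine, bias 3% | 1% | 43% | 61% | 56% | 36% |
| Creatinine, bias 0% | 90% | 86% | 78% | 66% | 40% |

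If the noise is shared equally by the two methods, the pass rate at 3% bias and SD 20% is 77% for both analytes.

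**Step 4: what those pass rates mean for patients, at 3% bias.**

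- SD 20%: limits 3 ± 1.96 × 20, or -36.2% to +42.2%. About 32% of patients have results more than 20% apart.
- SD 5%: limits 3 ± 1.96 × 5, or -6.8% to +12.8%. About 0.03% of patients have results more than 20% apart.

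The rule passes the first about half the time and the second about 1% of the time.

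**Step 5: an agreement criterion on the same cases.** Require the 95% CI for bias to lie within ±B% and the estimated limits of agreement within ±L% (20,000 replicates, 3% bias, limits purely illustrative).

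| (B, L) | SD 5% passes | SD 20% passes |
|---|---|---|
| (5, 20) | 79% | 0% |
| (7.5, 25) | 100% | 0% |
| (10, 30) | 100% | 0.2% |

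The order of the two methods is now the right way round.

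**The case against.** - **The protocol may hold acceptance limits.** It is not shown, so absence alone would not be a finding. But the SAP states a rule of its own, and that rule would conflict with any such limits.
- **The wording is tentative.** Interpretation speaks only of what is anticipated and could follow, and finger-prick results are not reported and change no dosing in the study. This stands, and the sentence is not an automatic gate. It is still the only condition given for remote use.
- **The SAP names no consequence if a difference is found.** Correct; recalibration is not excluded. A significant difference would nevertheless contradict the stated hypothesis and so count against a tight method.
- **The combined pass rule is constructed for this check.** Correct. The SAP defines none, and the figures move with the assumptions: 44% becomes 77% for tacrolimus at SD 20% when noise is shared equally.
- **More noise does not always help.** Correct. Once Passing-Bablok is added, pass rates at zero bias fall as scatter rises, and at 3% bias they rise and then fall. The bias-only figures in step 2 overstate the effect for the planned pair of analyses. What remains is that wide scatter still passes often, and more often than a tight method with a small bias.
- **A replacement criterion must say whether point limits or their CIs are judged.** This matters. With zero bias, SD 10% and (5, 20), the pass rate is 39% on point limits and 1.5% if the CIs must also lie inside.

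**Conclusion.** The concern holds: the SAP is wrong as written in its hypothesis, in the stated purpose of its analyses and in its condition for remote use. Naming Bland-Altman does not repair this, nor does the comparison with the published study, because neither carries a threshold. The conclusion follows from the text alone. The size rests on assumed SDs, biases, concentration ranges, venous CV, a 5% level and a pass rule that the SAP does not supply. Under those assumptions a method with limits of about -36% to +42% passes 44% to 77% of the time, and one with limits of about -7% to +13% passes about 1%. This should be corrected before the paired data are opened, because limits chosen afterwards would not be credible.

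**What to change.** Replace the hypothesis and the adoption sentence with one agreement criterion per analyte, for example:

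> Mitra sampling is regarded as interchangeable with the routine venous method for this analyte if the 95% CI for mean percent bias lies within ±B% and the estimated 95% limits of agreement lie within ±L%. The limits of agreement are reported with their 95% CIs.

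The laboratory and the renal team should set B and L separately for tacrolimus and creatinine before the paired data are opened. They may draw on the published figures the SAP already plans to use for comparison. The text should state, as above, that the point limits are judged and their CIs reported. Passing-Bablok slope and intercept should be reported with CIs as estimates, not used as a significance gate.

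The cost is SAP wording and one decision per analyte, with no extra patients or samples. The downside is that a widely scattered method can no longer pass by default and tight limits can fail a moderately scattered one: with B = 5 and L = 20, SD 10% and zero bias passes 39% of the time. If the CIs of the limits also had to lie inside, failure would be far more common: at 3% bias, SD 10% and (7.5, 25), the pass rate drops from 79% to 20%.
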